13.5 External Data and Safety Monitoring Board (DSMB)

The Principal Investigator and Sub-Investigators must comply with applicable federal, state, and local regulations regarding reporting and disclosure of potential conflicts of interest (COIs). Conflicts of interest may arise from situations in which financial or other personal considerations have the potential to compromise or bias professional judgment and objectivity. Conflicts of interest include but are not limited to royalty or consulting fees, speaking honoraria, advisory board appointments, publicly-traded or privately-held equities, stock options, intellectual property, and gifts.

The Duke Office of Scientific Integrity-Conflict of Interest Office (DOSI-COI) reviews and manages research-related conflicts of interest. The Principal Investigator and Sub-Investigators must report conflicts of interest annually and within 10 days of a change in status, and when applicable, must have a documented management plan that is developed in conjunction with the Duke Research Integrity Office (RIO) and approved by the IRB/ Institutional Ethics Committee (IEC).

14 QUALITY CONTROL AND QUALITY ASSURANCE

14.1 Monitoring

This clinical research study will be monitored both internally by the PI, and institutionally by the Duke Cancer Institute (DCI). In terms of internal review, the PI will continuously monitor and tabulate AEs. Appropriate reporting to the Duke University Medical Center IRB will be made. If an unexpected frequency of Grade 3 or 4 events occur, depending on their nature, action appropriate to the nature and

frequency of these AEs will be taken. This may require a protocol amendment, dose de-escalation, or potentially closure of the study. The PI of this study will also continuously monitor the conduct, data, and safety of this study to ensure that:

- Interim analyses occur as scheduled;
- Stopping rules for toxicity and/or response are met;
- Risk/benefit ratio is not altered to the detriment of the subjects;
- Appropriate internal monitoring of AEs and outcomes is done;
- Over-accrual does not occur;
- Under-accrual is addressed with appropriate amendments or actions;
- Data are being appropriately collected in a reasonably timely manner.

DCI Protocol Review and Monitoring systems (PRMS) review of this protocol begins with an initial review by the Protocol Review and Monitoring Committee (PRMC). PRMC new protocol review focuses on scientific relevance, study design, adequacy of biostatistical input, protocol prioritization, feasibility of completing the study within a reasonable time frame and risk assessment of the trial. The PI will abide by PRMC assessment of the level of risk, which will determine the intensity of subsequent DCI monitoring. PRMC also conducts annual scientific progress reviews on protocols that are open to enrollment and focus on protocol prioritization, accrual and scientific progress. These reviews are conducted at the time of IRB annual renewals and documentation of all PRMC reviews will be maintained in eIRB/iRIS systems.

A determination for the degree of monitoring conducted by the DCI monitoring team is made at the time of initial PRMC approval to commensurate with the type and level of intervention, phase, endpoints, degree of risk, size and complexity of the protocol. A formal, independent monitoring will be conducted by the DCI monitoring team according to the risk level and monitoring plan assigned by the PRMC until the study is closed to enrollment or subjects are no longer receiving study drug or other interventions that are more than minimal risk. Additional monitoring may be prompted by findings from monitoring visits, unexpected frequency of serious and/or unexpected toxicities, or other concerns. Monitoring visits may also be initiated upon request by DUHS and DCI Leadership, PRMC, SOCOMM, a sponsor, an investigator, or the IRB.

The DCI monitoring team reviews the adequacy of informed consent, enrollment of eligible patients, implementation of protocol-specified procedures and treatment, adequacy of data collection, and appropriateness of AE monitoring and reporting. The DCI monitoring team presents final monitoring reports to the DCI SOCOMM highlighting safety concerns and unresolved issues. The SOCOMM, at a convened meeting, assigns an overall rating of satisfactory, marginal, or unsatisfactory to reflect the overall quality of data, regulatory, consent, eligibility, study conduct and AE reporting. Corrective action plans (CAPs) are developed, implemented, and evaluated as indicated. The SOCOMM will notify the sponsor-investigator and DUHS IRB when significant safety concerns are identified.

The SOCOMM in concert with DCI monitoring team conducts data and safety monitoring for DUHS sponsor-investigator phase 1 and 2, therapeutic interventional

oncology studies that do not have an independent DSMB. These reviews occur at a minimum annually and more frequently for the high risk studies. The SOCOMM safety reviews include review of safety data, enrollment status, stopping rules if applicable, accrual, toxicities, reference literature, and interim analyses as provided by the sponsor-investigator. The SOCOMM, at a convened meeting, assigns a rating of satisfactory when adequate accrual with lack of excessive toxicity is present.

14.2 Audits

The Duke University Office of Audit, Risk and Compliance (OARC) may conduct confidential audits to evaluate compliance with the protocol and the principles of good clinical practice (GCP). The Principal Investigator (PI) agrees to allow the OARC auditor(s) direct access to all relevant documents and to allocate his/her time and the time of the study team to the auditor(s) in order to discuss findings and any relevant issues.

OARC audits are designed to protect the rights and well-being of human research subjects. OARC audits may be routine or directed (for cause). Routine audits are selected based upon risk metrics generally geared towards high subject enrollment, studies with limited oversight or monitoring, Investigator initiated Investigational Drugs or Devices, federally-funded studies, high degree of risk (based upon AEs, type of study, or vulnerable populations), phase 1 studies, or studies that involve Medicare populations. Directed audits occur at the directive of the IRB or an authorized Institutional Official.

OARC audits examine research studies/clinical trials methodology, processes and systems to assess whether the research is conducted according to the protocol approved by the DUHS IRB. The primary purpose of the audit/review is to verify that the standards for safety of human subjects in clinical trials and the quality of data produced by the clinical trial research are met. The audit/review will serve as a quality assurance measure, internal to the institution. Additional goals of such audits are to detect both random and systemic errors occurring during the conduct of clinical research and to emphasize “best practices” in the research/clinical trials environment.

14.3 Data Management and Processing

14.3.1 Case Report Forms

The electronic CRF (eCRF) will be the primary data collection document for the study and is developed in conjunction with statistical oversight. The CRFs will be updated in a timely manner following acquisition of new source data. Only the PI, the study coordinator, the data management team, and the clinical trials manager are permitted to make entries, changes, or corrections in the eCRF.

An audit trail will be maintained automatically by the electronic CRF management system. All users of this system will complete user training, as required or appropriate per DCI requirements and other regulations.

14.3.2 Data Management Procedures and Data Verification

Access to electronic databases will be managed by the PRTBTC Data Manager.

Completeness of entered data will be checked automatically by the eCRF system and users will be alerted to the presence of data inconsistencies. Additionally, the data management team and the statistical team will cross-reference the data to verify accuracy. Missing or implausible data will be brought to the attention of the PI requiring an appropriate response (i.e., confirmation of data, correction of data, completion or confirmation that data is not available, etc.).

The database will be reviewed and discussed prior to database closure, and will be closed only after resolution of all remaining queries. An audit trail will be kept of all subsequent changes to the data.

14.3.3 Study Closure

Following completion of the studies, the PI will be responsible for ensuring the following activities:

- Data clarification and/or resolution
- Accounting, reconciliation, and destruction/return of used and unused study drugs
- Review of site study records for completeness
- Shipment of all remaining laboratory samples to the designated laboratories.

15 STATISTICAL METHODS AND DATA ANALYSIS

All statistical analysis will be performed under the direction of the statistician designated in key personnel. Any data analysis carried out independently by the investigator must be approved by the statistician before publication or presentation.

15.1 Study Design Overview

Adults with newly diagnosed, primary GBM who are IDH wild type, have unmethylated MGMT promoter, and have undergone resection will be eligible for this study. Patients who meet eligibility criteria will be offered enrollment at the clinic visit after XRT/TMZ if they can start treatment within 8 weeks of XRT/TMZ completion (and as long as this is felt to be in the best interest of the patient by the treating physician). A maximum of 36 patients will be accrued to this study. After the initial dose escalation portion is complete, patients will be tested for CMV status however enrollment will be first come, first serve, and the slots will not be allocated based on CMV results.

All patients will receive P30-EPS vaccine (EphA2, pp65, and survivin peptides each linked to P30) suspended in 10% DMSO in water, pooled, and mixed with 20 µg/kg of Hiltonol®. All P30-EPS vaccines are given initially in a Priming Phase [on days 1, 4 (\pm 1 day), 8 (\pm 1 day), 15 (\pm 2 days), and 22 (\pm 2 days)], and then in a Booster Phase (on day 84 and day 140, both \pm 7 days).

The primary objective of this trial is to evaluate the safety of P30-EPS vaccines in patients with newly diagnosed GBM, while exploring the impact of the treatment regimen on the immunologic response of the patient.

15.2 Analysis Sets

Sections 15.5, 15.6 and 15.7 provide the statistical analysis plans to address each individual objective. Included in these analyses is a description of the analysis set, or the set of patients that will be considered in the planned analyses.

15.3 Patient Demographics and Other Baseline Characteristics

The clinical and sociodemographic characteristics of all patients treated will be summarized by dose level and CMV status using descriptive statistics (e.g., means/standard deviations, percentiles, frequencies).

15.4 Treatments

A frequency distribution of the number of vaccines a patient receives will be generated for each dose level within each CMV stratum.

15.5 Primary Objective

The primary objective of this trial will be to evaluate the safety profile of a cancer vaccine comprised of the universal epitope P30 linked to EphA2, CMV pp65, and survivin (P30-EPS) peptides.

Safety will be assessed within two separate strata (patients who are CMV seropositive and patients who are CMV seronegative) given our expectation that the AE profile among CMV seropositive patients and CMV seronegative patients may differ.

Within each stratum, a standard 3+3 study design will be used to escalate or de-escalate the vaccine dose. The starting dose of the P30-EPS vaccine is 300 µg/peptide/dose, and the dose will be escalated to 400 µg/peptide/dose. In the event that 300 µg/peptide/dose is deemed unsafe, the dose will be de-escalated to 200 µg/peptide/dose. If 200 µg/peptide/dose is not considered safe, then the P30-pp65 peptide may be removed from the vaccine combination; the protocol will be amended in consultation with the FDA to administer a vaccine without P30-pp65.

Section 15.5.1 describes the initial toxicity monitoring guidelines; whereas, Section 15.5.2 describe the overall monitoring guidelines. Section 15.5.3 describes other summaries of AEs that will be generated.

15.5.1 Dose Escalation / De-Escalation Guidelines

Within each stratum (CMV seropositive and CMV seronegative), cohorts of 3 patients will be accrued to the study in a manner similar to a standard phase 1 study to assess the toxicity associated with the vaccine consisting of EphA2, pp65, and survivin P30-EPS peptides linked to P30 (P30-EPS). Three dose levels are under consideration: 200 µg/peptide/dose (dose level minus 1), 300 µg/peptide/dose (dose level 1), and 400 µg/peptide/dose (dose level 2), with the starting dose being 300 µg/peptide/dose.

Within each stratum, the first 3 patients will be treated with 300 µg/peptide/dose. The enrollment of the first 2 patients treated with 300 µg/peptide/dose will be staggered by 2 weeks. After accrual of the first cohort of 3 patients, accrual will be temporarily suspended.

15.5.1.1 General Acute Monitoring Guidelines

The following monitoring guidelines apply to both the CMV seropositive and CMV seronegative strata. The period of acute toxicity monitoring begins with vaccine #1 and lasts until 30 days after vaccine #5.

- If 0 of the first 3 treated patients within a stratum experience a DLT during the observation period beginning at vaccine #1 and ending 30 days after vaccine #5, or 1 of 6 treated patients within a stratum experiences a DLT, then patient accrual will be re-initiated. If the current dose level is 300 µg/peptide/dose, the next cohort of patients will be treated at 400 µg/peptide/dose. Otherwise, subsequent patients will be treated at the same dose level. The maximum dose at which 0 of 3, or 1 of 6 patients experience a DLT during priming will be the MTD.
- If 1 of the first 3 treated patients within a stratum experiences a DLT during the observation period beginning at vaccine #1 and ending 30 days after vaccine #5, an additional cohort of 3 patients will be treated within the same stratum at the same dose level.
- If 2 of the first 3 or 6 treated patients experience a DLT during the observation period beginning at vaccine #1 and ending 30 days after vaccine #5, the next cohort of patients within that stratum will be treated at a lower dose. Treatment modifications for the CMV seropositive stratum are described below in Section [15.5.1.2](#).
- The MTD is the highest dose level at which 0/3 or 1/6 patients experience a DLT.

If a patient withdraws from the study before completion of the observation period that ends 30 days after vaccine #5 for a reason unrelated to the occurrence of a DLT, the patient will be replaced for the purpose of this initial acute safety monitoring. This patient will remain a part of all other analyses, if possible.

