9.1.2.2 Definition of Dose Limiting Toxicity (DLT)

As defined in Section 9.1.2.1, a DLT is as an unacceptable toxicity that occurs during the DLT observation period that extends between vaccine #1 and 30 days after vaccine #5.

Patients receiving less than 5 vaccines without experiencing a DLT will be replaced in the decision-making concerning dose escalation.

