15.5.2 Overall Toxicity Monitoring Guidelines

With vaccinations potentially being administered through day 140, we will be monitoring within each stratum for the occurrence of unacceptable toxicities throughout vaccine treatment.

Tabulated below ([Table 4](#)) are the conditions under which accrual to a stratum will be temporarily suspended and data carefully reviewed to determine if accrual should be continued or terminated, and whether elements of the treatment regimen should be modified. Accrual will also be suspended whenever a death occurs that is possibly, probably, or definitely related to vaccine treatment.

Table 4: Conditions for Temporary Accrual Suspension

Number of Patients Within CMV Stratum Treated at a Particular Dose Level	Number of patients with unacceptable toxicity
0-6	≥2
7-9	≥3
10-14	≥4
≥15	≥5

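### The dose-decision bullets in 15.5.1.1 do not match the per-dose MTD definition, the standard 3+3 design or Table 4 (minor; a few words fix it)

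*Combined protocol and SAP*

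**What the plan says.** Section 15.5 names a standard 3+3 design, run separately in CMV-seropositive and CMV-seronegative patients. It starts at 300 µg/peptide, with 400 above and 200 below. Section 15.5.1.1 turns this into bullets:

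- **Bullet 1 (pass).** A stratum passes with no DLT in its first 3 patients, "or 1 of 6 treated patients within a stratum experiences a DLT, then patient accrual will be re-initiated". From 300, "the next cohort of patients will be treated at 400" µg. From any other level, "Otherwise, subsequent patients will be treated at the same dose level".
- **Bullet 2 (expand).** "If 1 of the first 3 treated patients within a stratum experiences a DLT", three more patients are treated in that stratum at the same dose.
- **Bullet 3 (step down).** "If 2 of the first 3 or 6 treated patients experience a DLT", the next cohort in that stratum receives a lower dose.
- **Bullet 4 (MTD).** "The MTD is the highest dose level at which 0/3 or 1/6 patients experience a DLT".

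Three other places bear on these rules. Table 4 in 15.5.2 suspends accrual by counts whose unit is "Number of Patients Within CMV Stratum Treated at a Particular Dose Level"; for 0-6 patients the threshold is at least 2 with unacceptable toxicity. Section 9.1.2.2 makes every DLT count there, since "a DLT is as an unacceptable toxicity that occurs during the DLT observation period". Section 15.5.1.3 treats further patients at the MTD once it is determined.

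**The concern.** These bullets choose the dose for the next patients. They also fix the MTD, which defines the immunogenicity analysis sets in 15.6.1 to 15.6.4. Such a rule should give one action for each outcome, and the action should agree with the MTD definition. Bullets 1 and 2 count over the stratum, while the MTD definition, the primary endpoint in Section 8 and Table 4 all count by dose level. Bullet 1 has no memory of a failed 400 level. Bullet 3 states an exact count where a minimum is meant. At stake are the stop after six patients at 400 in (a), a possible return to a dose that has failed in (b), and agreement with Table 4 in (c).

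**Working it through.** The plan states no operating characteristics for the 3+3 rule, so there is no figure to reproduce. The check is to follow the bullets literally and compare each result with the rest of the plan.

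| Course in one stratum | Bullets as worded | MTD definition, standard 3+3, other sections |
|---|---|---|
| (a) 0/3 at 300, then 1/3 at 400 | Stratum total is 0 + 1 = 1 DLT in 3 + 3 = 6 patients, so bullet 1 is met. Bullet 2 is not, because the stratum's first 3 had no DLT. Accrual reopens at 400. | 400 stands at 1/3, neither 0/3 nor 1/6. Three more patients at 400, then a decision at six. |
| (b) 400 has failed, stratum is back at 300, and 300 stands at 1/6 | Bullet 1 is met with current level 300, so the next cohort goes to 400. | 300 is the highest level that qualifies, so it is the MTD, and 15.5.1.3 keeps patients there. |
| (c) 3/3, or 3 or more of 6, at one level | The count is not 2, so bullet 3 is not literally met. | Table 4 says at least 2. After a failure at 400, the MTD definition with 15.5.1.3 gives 300. After a failure at 300, 15.5 gives 200. |

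In (a) the next dose is 400 on either reading; what is lost is the fixed stop after six. Fault (b) does not depend on pooling, since it arises with counts taken strictly per dose. Two courses lead to it: 0/3 at 300, failure at 400, then 1/3 in the next cohort at 300; or 1/6 at 300 first, then failure at 400.

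A related gap is 0/6. If 300 gives 0/3, 400 fails, and three more at 300 have no DLT, the result is literally neither 0/3 nor 1/6, although it is better than 1/6.

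**Illustration only.** The documents give no DLT rates. Assume true rates at 300/400 of 10%/30% and 20%/40%. Let b(k,p) be the binomial probability of k DLTs in 3 patients. A level fails with probability fail(p) = 1 − b(0,p) × [1 + b(1,p)], which is 0.506 at 30% and 0.691 at 40%.

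- Course (a), b(0,p300) × b(1,p400): 0.729 × 0.441 = 0.32; 0.512 × 0.432 = 0.22.
- Course (b), both routes, 2 × b(0,p300) × b(1,p300) × fail(p400): 2 × 0.729 × 0.243 × 0.506 = 0.18; 2 × 0.512 × 0.384 × 0.691 = 0.27.
- Course (c) once 400 is opened, b(3,p) + b(1,p) × [b(2,p) + b(3,p)]: 0.027 + 0.441 × 0.216 = 0.12; 0.064 + 0.432 × 0.352 = 0.22.

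These are chances that a stratum meets an outcome the wording mishandles. They show only that such outcomes are ordinary in a 3+3 design.

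**The case against.** The strongest reply is that nobody would apply the bullets this way. If the first 3 patients in a stratum are counted regardless of dose, they are always the first three at 300, and the rule could never judge the first cohort at 400. Bullet 1 refers to the current dose level, bullet 2 keeps the same dose, and 15.5 names a standard 3+3. Section 15.5.1.3 opens expansion only when the MTD is known, and at 1/3 the 400 level is not yet the MTD. Table 4 also suspends accrual at 2 or more events in up to 6 patients at a dose, so a failed 400 has normally been reviewed before anyone could return to it.

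Most of this stands, and it is why the point is minor. It does not remove the faults. Table 4 names no next dose. Its threshold rises to 3 at 7-9 patients, so it replaces the stop lost in (a) only if the second DLT is recorded before the seventh patient at 400 starts. The DLT window is long: vaccine #5 on day 22 plus 30 days runs to about day 52. For (b), the reply shows that other sections overrule bullet 1, which concedes that bullet 1 is wrong as written.

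Three stronger readings are tempting, and the documents support none of them. First, a reader might infer from (c) that 3/3 or 3/6 at 400 leaves the stratum with no dose. It does not: 400 is reached only after 300 has passed, so the MTD definition and 15.5.1.3 put the stratum at 300. Second, a reader might take the illustrative percentages as chances of a wrong MTD. They are chances of ordinary courses under assumed rates. Third, 10.1.4 shows that a second set of 6 patients was being monitored for DLTs, which might suggest that the rule has already been misapplied. That section gives neither doses nor DLT counts, so nothing can be said on this.

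**Conclusion.** The point holds as a wording error in a dose-decision rule, of minor severity. Fault (a) contradicts the plan's own unit of counting and, read literally, skips the second cohort and the decision at six. Fault (b) conflicts with the MTD definition and 15.5.1.3 even on the intended per-dose reading. Fault (c) is a threshold wording error only. A wrong MTD is unlikely because the intended rule can be inferred and Table 4 provides a pause. The conclusion rests on the text alone; the probabilities depend on assumed DLT rates and carry no weight in it.

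**What to change.** Amend 15.5.1.1 as follows:

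1. In every bullet, count *of patients treated at the current dose level within the stratum*.
2. In bullet 3, write *at least 2 of the first 3 or 6*.
3. In bullet 1 and both statements of the MTD, write *0 or 1 of 6* in place of 1 of 6, keeping 0 of 3.
4. Add to the escalation sentence: *unless 400 has already met the de-escalation rule, in which case the stratum stays at 300 as long as 300 still meets the MTD definition*.

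The added clause does not require six patients at 300; the plan accepts 0/3 there now and still would. The cost is a few words in one section. The maximum of 36 patients, the visits and the procedures are unchanged.
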